8.2 Subgroup analyses

We will stratify the adjusted model by potential effect modifiers, and will add these covariates to adjusted models as interaction terms with diet group independently, using likelihood ratio tests comparing regression models with and without interaction terms to test for effect modification.

To investigate the role of diet quality as a potential effect modifier, participants will be dichotomised into higher and lower AHEI adherence groups at the median AHEI score in the overall sample to maximise power in each diet group sub-strata. We will also assess the interaction between diet groups and a five-unit increase in AHEI score on hip fracture risk. Other potential effect modifiers include age (continuous and split at < 60 years, ≥ 60 years), sex (male, female), and BMI (continuous and split at < 18.5, 18.5-24.9, and ≥ 25 kg/m² if there is enough power).

The adjusted model will also be further stratified by specific single-nucleotide polymorphisms (SNPs) of genes with a plausible relationship with hip fracture risk and diet (PPAR γ , VDR, MTHFR, CYP24A1, CYP27B1, and IGF-1) to explore potential gene-diet interactions.

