8.1.2 Relative risk

Cox regression models will be applied to estimate HR (95% CI's) for associations between each diet group and hip fracture risk, with regular meat-eaters as the reference group. The proportional hazards assumption will be assessed based on Schoenfeld residuals.

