8.1.3 Accounting for confounding

Unadjusted and adjusted cox models will be applied. Both will control for age by using attained age as the timescale. The adjustment set for the adjusted model will be informed by a DAG model, which will be constructed using the online tool DAGitty, following available guidelines on their use (3). Confounders will be considered as covariates that are 1) risk factors of the outcome; 2) associated with the exposure; and 3) not on the causal pathway (4). Potential confounders are age at recruitment, sex, region, ethnicity, socio-economic status or education, marriage, physical activity, smoking, alcohol, BMI (or height and weight), number of children, menopausal status, hormone replacement therapy (HRT) in postmenopausal women, chronic disease prevalence at recruitment, and use of nutritional supplements (either generic or supplement-specific e.g. for calcium, vitamin D, and fish oil in particular, depending on availability of data). A list of likely confounders and their derivation is summarised in Supplementary Table 1.

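### The pooled diet-by-age interaction test has no sex-specific baseline hazard or sex-by-age term, so a sex effect that changes with age can partly appear as modification of diet by age

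*SAP*

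**What the plan says.** SAP Section 8.1.3 sets the timescale for the unadjusted and adjusted models: "Both will control for age by using attained age as the timescale". Sex appears there in a list of candidates for the adjustment set: "Potential confounders are age at recruitment, sex, region, ethnicity", and so on. The list also contains menopausal status and HRT. Nothing says that sex will define strata of the baseline hazard.

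Section 8.1.2 states: "The proportional hazards assumption will be assessed based on Schoenfeld residuals". It does not say what follows if the check fails.

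Section 8.2 does two things. It fits the model within levels of each modifier: "We will stratify the adjusted model by potential effect modifiers". It also "will add these covariates to adjusted models as interaction terms with diet group independently", and judges modification by a likelihood ratio test of the fit with those terms against the fit without them. The modifiers include "age (continuous and split at < 60 years, ≥ 60 years), sex (male, female"). No product of sex with age appears in either of the models being compared.

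**The concern.** A likelihood ratio test for diet-by-age is valid only if the model without that term is adequate. On a plain reading, that model gives sex one coefficient at every attained age, apart from what menopausal status and HRT absorb. Recruitment was at 40-69 years and English follow-up runs to September 2021, so attained age runs from 40 to the early 80s.

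Two conditions together cause trouble:

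1. The share of women differs between diet groups. The SAP's own confounder rule in Section 8.1.3 requires association with the exposure, so listing sex implies some difference.
2. The women/men hazard ratio for hip fracture changes with age. Listing menopausal status and HRT makes this plausible but does not establish it.

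A diet group with more women then shows a hazard that drifts with age relative to regular meat-eaters. With no sex-by-age term available, the diet-by-age terms take up part of the drift. Modification by age is a secondary objective (Section 1.2) and p < 0.05 counts as significant (Section 8.4), so a difference in sex mix could be reported as a diet finding.

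**Working it through.** **The plan's own figures first.** The SAP gives no power or error rate for the interaction tests. Its minimum detectable hazard ratios (Table 3) can be reproduced from the group sizes in Section 6.0, pairing each group with regular meat-eaters at 3% events:

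HR = exp[(1.960 + 0.842) / (SD × √events)], with SD = √[p(1 − p)].

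- Occasional: events 0.03 × (247,571 + 205,385) = 13,589; SD 0.498; HR 1.049 (SAP 1.05).
- Pescatarian: events 0.03 × 258,267 = 7,748; SD 0.199; HR 1.173 (SAP 1.17).
- Vegetarian: events 0.03 × 256,256 = 7,688; SD 0.181; HR 1.193 (SAP 1.19).

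The sizes and incidence are therefore used below as the SAP uses them. Regular and occasional meat-eaters are 452,956 of 472,337, or 96%, so the contrast between them dominates the test.

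**Inputs from the SAP.** Group sizes; 3% incidence (0.03 × 472,337 ≈ 14,170 events), with 1% as an alternative; recruitment age 40-69; about 12 years of follow-up; two-sided 5% level. Four diet groups and one linear or binary age term give a 3-df test.

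**Assumed inputs, not in the SAP.**

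- Women's share in regular/occasional/pescatarian/vegetarian: moderate 50/58/62/60%, large 45/62/70/66%.
- Women/men HR at age 55 and at 80: from 1.2 rising to 1.8, up to 0.7 rising to 2.0.
- True diet HR of 1 at every age.

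**Size of the leak by hand.** If the true sex log HR g(a) is fitted as a constant, the occasional-versus-regular log HR drifts with age by about (difference in women's share) × (change in g). Over 10 years, the change in g is ln(HR80/HR55) × 10/25.

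| Women/men HR, 55 to 80 | Change in g per 10 y | Moderate (0.58 − 0.50 = 0.08) | Large (0.62 − 0.45 = 0.17) |
|---|---|---|---|
| 1.2 to 1.8 | 0.405 × 0.4 = 0.162 | exp(0.013) = 1.013 | exp(0.028) = 1.028 |
| 1.0 to 2.0 | 0.693 × 0.4 = 0.277 | exp(0.022) = 1.022 | exp(0.047) = 1.048 |
| 0.7 to 2.0 | 1.050 × 0.4 = 0.420 | exp(0.034) = 1.034 | exp(0.071) = 1.074 |

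These agree with fitted spurious HR ratios of 1.01-1.07 per 10 years of age without a menopause term.

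**Rejection rate of the test.** Expected events were built by diet group, sex, entry age and attained age. Poisson models with attained-age dummies, the large-sample equivalent of Cox regression on attained age, were fitted with and without diet-by-age terms. The drop in deviance is the noncentrality λ, and the rejection rate is P[χ²₃(λ) > 7.81].

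| 3% incidence | Moderate sex difference | Large sex difference |
|---|---|---|
| No menopause term | 6-15% | 11-52% |
| Menopause term included | 6-10% | 9-34% |
| Baseline stratified by sex | 5.0% (λ = 0.000) | 5.0% (λ = 0.000) |

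The no-menopause row for the moderate case was run at half the large sex differences, which is nearly the same mix. Equal sex mix gives 5.0% however strongly the sex effect changes with age. A constant sex effect gives 5.0% whatever the mix.

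A second calculation used slightly different assumptions (shares up to 45/62/72/67%; sex HR paths from age 45 to 80). With a menopause term it gave 5.3-9.4% (moderate) and 6.5-29% (large). At 1% incidence, its unequal-mix scenarios ran from 5.1% to 22%. HRT was not modelled in these fits.

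**What is not affected.** The main diet HRs move by less than 1.2%. The diet-by-sex test rejects 5-10% of the time. Within an age group the model has its own sex coefficient, so the age-stratified HRs are largely protected.

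**The case against.** The strongest reply is that the SAP does not commit to a single sex effect. Sex is one candidate for a DAG-informed set, and menopausal status and HRT apply only to women and depend on age, so they already act as partial sex-by-age terms. This stands in part: the menopause term roughly halves the noncentrality. It does not close the gap. Section 11.1.4 fixes menopausal status at recruitment, and women of 55 or over who are unsure count as postmenopausal. The term is therefore close to constant among older women and cannot follow a sex effect that changes at later ages.

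Second, the planned Schoenfeld check would expose the problem. On an attained-age scale it tests exactly whether the sex HR changes with age. Under the assumed paths, without a menopause term, the expected z is 6.7-18.9 at 3% incidence and 3.9-10.9 at 1%, with power of at least 97%. This also stands, provided the check covers sex. But detection without a stated response leaves the interaction test as specified.

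Third, the age-stratified HRs will be presented alongside the pooled p-value, so a reader could notice a disagreement. That is true, but the p-value is what the SAP uses to declare modification.

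A reader might also infer that the pooled p-value and the stratified HRs should come from the same model, and that adding products of each modifier with age at recruitment and BMI would achieve this. That does not follow. Separate stratum fits free every covariate and the baseline hazard, which a few added products do not. No calculation supports those products, and sex stratification alone removes the spurious signal examined here.

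**Conclusion.** The point holds as a conditional weakness of one pooled secondary test. As specified, the diet-by-age likelihood ratio test can exceed its nominal 5% level when the sex mix differs by diet group and the women/men hazard ratio changes with age. With a menopause term at 3% incidence, the excess ranges from slight (6-10%, moderate sex difference) to material (9-34%, large). It is smaller at 1% incidence, and zero if either condition fails. The sex shares and the sex HR paths are assumptions; the SAP supplies neither.

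A reader might infer that any age-dependent sex effect will be read as diet modification, or that even a small sex difference dominates the test. The SAP does not support this. It gives no sex mix, no sex HR by age and no final covariate set, and only part of the change leaks through. The primary objective is not threatened.

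**What to change.** In Sections 8.1.2 and 8.1.3, state that all Cox models are fitted with the baseline hazard stratified by sex (in Stata, stcox with strata(sex)). In Section 8.2, keep that stratification in both models of each likelihood ratio test. Diet-by-sex terms remain estimable. Equivalently for the diet-by-age test, include a sex-by-age term in both models; this gave the same result to three decimals. If sex is kept as a covariate, also state what follows when the Schoenfeld check fails for it.

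The cost is a sentence or two of SAP text and one software option. The HR for sex is no longer estimated under stratification, but it is not an objective. Precision is essentially unchanged: the standard error of the occasional-versus-regular log HR is 0.0173 with sex as a covariate and 0.0174 with sex as a stratum.

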1.2 Secondary objectives

- To determine the roles of potential modifying factors on associations between each diet group and hip fracture risk, including age, sex, body mass index (BMI), and adherence to the Alternative Healthy Eating Index (AHEI).
- To investigate interactions between diet groups and genotypes on bone mineral density (BMD) and hip fracture risk.
- To determine the roles of potential mediating factors on any observed associations between diet groups and hip fracture risk, including the roles of BMI, measures of body composition measures, circulating levels of vitamin D and IGF-1, and dietary intake of protein, calcium, vitamin B12, and omega-3 fatty acids.

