4.2 Exposure assessment

Participants will be classified into diet groups based on responses to questions in the touchscreen food frequency questionnaire (FFQ) completed at recruitment that relate to meat, fish, eggs, or dairy consumption. These included questions on frequency of intake of oily fish, non-oily fish, processed meat, poultry, beef, lamb/mutton, pork, eggs, and dairy products. Questions on meat and fish were asked in the form of “how often do you eat [specific food or beverage?]” or similar. Valid options were 1 “never”, 2 “less than once a week”, 3 “once a week”, 4 “2-4 times a week”, 5 “5-6 times a week”, or 6 “once or more daily”. We will convert responses to these individual questions into weekly-based consumption frequencies as follows: 0, 0.5, 1, 3, 5.5, 7 servings/week.

We will sum responses to questions on intake of processed meat, poultry, beef, lamb/mutton, and pork to form total meat intake (servings/week); and questions on intake of oily and non-oily fish intake to form total fish intake (servings/week). Intake of eggs and dairy products was assessed by asking

participants “Which of the following do you never eat?”, with options of “Eggs or foods containing eggs”, “Dairy products”, “I eat all of the above”, or “Prefer not to answer”.

Diet groups will be regular meat-eaters (ate meat \geq 5 times/week), occasional meat-eaters (ate meat $<$ 5 times/week), pescatarians (reported never eating meat but ate fish), vegetarians (reported never eating meat or fish but did consume eggs or dairy products), and vegans (reported never eating meat, fish, eggs, or dairy products).

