Component	Criteria for minimum score (0)	Criteria for maximum score (0)	Component derivation
Vegetables, servings/day	0	≥ 5	Participants were asked in the touchscreen questionnaire at recruitment how many heaped tablespoons of cooked vegetables and raw vegetables/salad they ate per day, respectively. These will be summed to give total vegetable intake, and two heaped

			tablespoons will be considered as one serving of vegetable intake.
Fruit, servings/day	0	≥ 4	Participants were asked in the touchscreen questionnaire at recruitment how many pieces of fresh fruit and dried fruit they ate per day, respectively. These will be summed to give total fruit intake. One piece of fresh fruit and two pieces of dried fruit will each be considered a serving of fruit, respectively.
Wholegrains, g/day			Intake of wholegrains (g/day) has been previously calculated using 24-hour dietary recall data, and will be used in this study.
Women		75	
Men		90	
Sugar-sweetened beverages and fruit juice, servings/day	≥ 1	0	Intake of sugar-sweetened beverages and fruit juice (both in g/day) have been previously calculated using 24-hour dietary recall data. Each will be divided by standard portion sizes, then will be summed to give total intake of sugar-sweetened beverages and fruit juice (servings/day)
Nuts and legumes, servings/day	0	≥ 1	Intakes of legumes and pulses, salted nuts and seeds, and unsalted nuts and seeds (each in g/day) have been previously calculated using 24-hour dietary recall data. Each will be divided by standard portion sizes, then will be summed to give nuts and legumes intake (servings/day).
Red/processed meat, servings/day	≥ 1.5	0	Participants were asked in the touchscreen questionnaire at recruitment how often they ate processed meat, beef, lamb/mutton, and pork, respectively. Responses to these questions will be converted to daily-based consumption frequencies, and will be summed

			to give total red and processed meat intake in servings per day
Trans fat, % of energy	≥ 4	≤ 0.5	Trans fat intake (g/day) and total energy intake (kJ/day) have been previously estimated using 24-hour dietary recall data. We will calculate trans fat (% energy) using these two s, and conversion rates of 1 kJ = 4.184 kcal and 1 g trans fat = 9 kcal, respectively.
omega-3 fats (EPA +DHA), mg/day	0	250	Omega-3 fatty acid intake (g/day) has been previously estimated using 24-hour dietary recall data.

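### The AHEI tested as an effect modifier contains part of the exposure: its red/processed meat component is scored from four of the five meat items that define diet group, and the power rationale for the overall-median split is unsupported

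*SAP*

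**What the plan says.** SAP 1.2 sets a secondary objective: "To determine the roles of potential modifying factors on associations between each diet group and hip fracture risk". Adherence to the AHEI is one of the factors it names.

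SAP 8.2 gives two AHEI analyses. In the first, "participants will be dichotomised into higher and lower AHEI adherence groups at the median AHEI score in the overall sample to maximise power"; the sentence goes on to claim this for the sub-strata of each diet group. The second is continuous: "We will also assess the interaction between diet groups and a five-unit increase in AHEI score on hip fracture risk". Interactions are tested by likelihood ratio.

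Diet group comes from the recruitment touchscreen questionnaire. SAP 4.2: "We will sum responses to questions on intake of processed meat, poultry, beef, lamb/mutton, and pork to form total meat intake". Responses become "weekly-based consumption frequencies as follows: 0, 0.5, 1, 3, 5.5, 7 servings/week".

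The AHEI component table in SAP 11.1.3 derives red/processed meat from the same questionnaire, asking "how often they ate processed meat, beef, lamb/mutton, and pork, respectively". It gives the minimum score at 1.5 or more servings/day and the maximum at none. The text above that table awards up to 10 points for each of 11 components, 110 in total, and notes that the AHEI may differ between diet groups.

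No section mentions the shared items, removes the component, or lists a check on it among the sensitivity analyses in 8.4.

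**The concern.** An effect modifier should be definable separately from the exposure whose effect it is meant to modify. Here four of the five meat questions enter both. A meat-eater can raise the AHEI by eating less red or processed meat, which is also a move along the exposure scale. A pescatarian or vegetarian cannot, because that component is already at its ceiling.

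Two consequences follow. A vegetarian and a regular meat-eater with the same AHEI will generally have different scores on the other ten components, so the stratum-specific hazard ratios mix the amount of meat with the quality of the rest of the diet. And the interaction coefficient compares a five-unit step that may include meat in some groups with one that cannot in others. What is at stake is how a finding, positive or null, on the AHEI part of the objective in 1.2 can be read.

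Separately, the reason given for the cut-point does not follow. A median of the whole sample balances the whole sample. It balances a small diet group only if that group has the same AHEI median as everyone else.

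**Working it through.** **1. The SAP's own power figures.** Inputs from SAP 6.0: 247,571 regular meat-eaters, 205,385 occasional, 10,696 pescatarians, 8,685 vegetarians; 3% incidence; 80% power; p < 0.05 (two-sided, SAP 8.4). Formula: HR = exp[(1.960 + 0.842) / (SD × √events)], SD = √[p(1 − p)], with each group paired with regular meat-eaters.

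| Group | SD | HR recomputed | HR in Table 3 |
|---|---|---|---|
| Occasional | 0.498 | 1.050 | 1.05 |
| Pescatarian | 0.199 | 1.173 | 1.17 |
| Vegetarian | 0.181 | 1.193 | 1.19 |

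These three rows reproduce, so the same method is used in step 4. The SAP gives no figure for AHEI strata or interactions.

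**2. The overlap.** Anchors: 10 points at 0 servings, 0 points at 1.5/day = 10.5/week. Assuming linear scoring between them, score = 10 × (1 − r/10.5) for r red/processed servings/week. At r = 2, 5 and 7 this gives 8.1, 5.2 and 3.3.

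The lowest non-zero item code is 0.5/week, which is more than once a month (12/52 ≈ 0.23/week). Anyone meeting the pescatarian or vegetarian definition therefore has all five meat items at 0. Enumerating all 6⁵ response patterns gives:

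| Group | Possible component score |
|---|---|
| Pescatarian, vegetarian | 10 only |
| Occasional meat-eater | 5.71–10 (highest possible red/processed total is 4.5/week) |
| Regular meat-eater | 0–10 (10 if poultry only) |

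A five-unit AHEI step can thus consist wholly of meat in a regular meat-eater (5.25 servings/week), at most 10 − 5.71 = 4.29 points of meat in an occasional meat-eater, and no meat in the other two groups. The EPA+DHA component is a further, looser link: it reflects fish intake, which separates pescatarians from vegetarians, but it is derived from the 24-hour recall and not from the exposure items.

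**3. What this could do to the strata (illustration).** The SAP gives no AHEI distribution. Assume the non-meat score has SD 10 and the same mean in every group, with red/processed meat uniform on 3–12/week in regular and 0.5–4/week in occasional meat-eaters. Then about 68% of vegetarians and 41% of regular meat-eaters fall above the overall median. Within strata the vegetarians' non-meat score is about 4–5 points lower. With a milder meat range (2–8 and 0.5–3/week) that gap is about 3 points.

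In a separate simulation (meat-eaters' component mean 5.5, SD 2.5; non-meat SD 12 to 8, independent of diet group), 65–71% of non-meat-eaters lie above the overall median with the component included and 50% with it removed. The component carries 4–8% of AHEI variance among meat-eaters.

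**4. The median split.** Meat-eaters are (247,571 + 205,385)/472,337 = 95.9% of the sample, so the overall median is essentially theirs. If the small groups are shifted upward by 2, 5 or 8 points (assumed; SD 12 to 8), 56–60%, 65–73% or 74–83% of them lie above it.

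Vegetarian events number 0.03 × 8,685 ≈ 261. Minimum detectable HR, vegetarian against regular meat-eater, with regular meat-eaters split in half:

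| Vegetarians high/low | Events in low stratum | HR high | HR low | Ratio of HRs |
|---|---|---|---|---|
| 50/50 | 130 | 1.28 | 1.28 | 1.42 |
| 70/30 | 78 | 1.24 | 1.38 | 1.47 |
| 80/20 | 52 | 1.22 | 1.48 | 1.55 |

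These use the full cohort. Several components need 24-hour recall data, so actual counts may be smaller.

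**The case against.** The case for leaving the plan alone has several parts.

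*Only one component of 11 overlaps.* True: it is 10 of 110 points, and poultry is outside it. The other components can still vary within every diet group, and in the simulations both strata are populated in every group. A reader might infer that the modification objective cannot be answered at all; the SAP does not support that. The interaction is estimable, and the defect is in what it means.

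*The objective names the AHEI itself.* SAP 1.2 specifies adherence to that index, and 11.1.3 adopts it as the index of diet quality. No section asks in so many words whether a better vegetarian diet is protective. A score without meat is a non-standard index. This stands as a reason to keep reporting the full score, but not for drawing conclusions about diet quality from that score alone.

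*The illustration is fragile.* This also stands. If vegetarians score 4 or 5 points lower on EPA+DHA, about 52% or 49% of them lie above the median and their imbalance disappears. If their non-meat diet is truly 10 points better, the high-stratum gap reverses (11.5 against 9.5). So it cannot be stated as fact that vegetarians are compared in each stratum with meat-eaters whose other foods are better.

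*A common cut-point is sensible, and the continuous analysis needs none.* Both are correct. High AHEI then means the same score in every group, and group-specific medians would lose that. But this is a different justification from the one in 8.2, and the continuous analysis still uses the score containing the meat component.

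**Conclusion.** The point holds as one of interpretation. The overlap is certain from the SAP's own definitions: four of five exposure items score 10 of the 110 AHEI points, and the component is constant in pescatarians and vegetarians and variable only in meat-eaters. The score ranges assume linear scoring between the stated anchors. AHEI strata and the five-unit interaction therefore partly reflect the exposure, and diet quality is not the same quantity across groups. The objective is blurred, not lost.

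Neither the size nor the direction of any resulting bias can be established from the SAP; the percentages and within-stratum gaps above are illustrations under stated assumptions.

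The claim that the overall median maximises power in each diet group's sub-strata is unsupported. Its practical cost is modest: at an assumed 70/30 split the detectable ratio of hazard ratios is 1.47 instead of 1.42, although the low stratum alone goes from 1.28 to 1.38. A reader might infer that the split is bound to be unbalanced in the small groups. That is plausible, since the SAP itself allows that the AHEI may vary by diet group, but without AHEI distributions it is not shown.

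**What to change.** In SAP 8.2:

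- Repeat the dichotomised and five-unit AHEI interaction analyses with an AHEI that leaves out the red/processed meat component (range 0–100), and, as a check, with one that also leaves out EPA+DHA (0–90).
- Report these beside the full 110-point score, and state in advance that any conclusion about diet quality as a modifier rests on the meat-free score.
- Keep a cut-point common to all groups, but replace the power rationale with comparability: higher and lower adherence then mean the same score in each diet group.
- Report hip fracture cases by diet group within each AHEI stratum.

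The cost is a few sentences of SAP text and an extra derived score (plus its variant for the check), built from data already to be used. The downside is a score less comparable with the published index, which is still reported.

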8.4 Sensitivity analyses

1. An adjusted model with BMI removed from the adjustment set will be presented to determine the contribution of weight management to any associations.
2. We will present an adjusted model with vegans and vegetarians separated to determine if excluding vegans from the vegetarian group alters potential associations with hip fracture risk.
3. Online follow-up 24-hour dietary recall data will be compared with touchscreen FFQ data at recruitment to check for changes in diet group over time. In cases of substantial exposure change over time (e.g., > 10% of participants changing their dietary group), models will be repeated restricted to participants who maintained their original diet group.
4. Excluding cases occurring in the first three years of follow-up to check for reverse causality.
5. Excluding participants on long-term treatment for illnesses at recruitment who may be generally unhealthier and therefore at a higher risk of hip fracture.

6. We will explore patterns of missing covariate data, and will use multiple imputation through Stata's 'mi' package in the event of substantial missing covariate data.

All analyses will be performed using Stata. Two-sided p values < 0.05 will be considered statistically significant. All analyses performed and effect sizes computed will be presented in resulting manuscripts to avoid bias in selection of the reported result.

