11.1 Covariate classification

11.1.1 Socio-demographics

Age at recruitment

Calculated as date of recruitment minus date of birth, truncated to whole year.

Sex

Genetic sex as determined from genotyping analysis.

Region

At recruitment, participants attended one of 22 assessment centres across the UK. We will group the centres into three regions as follows: England (Barts, Birmingham, Bristol, Bury, Croydon, Hounslow, Leeds, Liverpool, Manchester, Middlesbrough, Newcastle, Nottingham, Oxford, Reading, Sheffield, Stockport, Stoke), Scotland (Edinburgh, Glasgow), and Wales (Cardiff, Swansea, and Wrexham).

Ethnicity

At recruitment, participants were asked in the touchscreen questionnaire to select their ethnic group among "White", "Mixed", "Asian or Asian British", "Black or black British", "Chinese", "Other ethnic group", "Do not know", or "Prefer not to say". We will regroup participants into the following ethnicity categories: White, Mixed race, Asian, Black, Other, and Unknown.

Socio-economic status

Townsend deprivation index will be used to represent socio-economic status. This variable has been created in the UK biobank based on the preceding national census output areas. Each participant was assigned a score corresponding to the output area in which their postcode was located. Participants

will then be split into quintiles from least deprived (Q) to most deprived (Q5), with an additional category for missing data (where postcode information was not provided).

Living alone

In the touchscreen questionnaire at recruitment, participants were asked “Including yourself, how many people are living together in your household?”. From this, we will define the variable “live alone” (with options yes, no, unknown).

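### The gene-diet analysis leaves the SNP list open, sets no multiplicity rule and controls ancestry only through broad self-reported ethnicity

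*SAP*

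**What the plan says.** Section 1.2 lists among the secondary objectives: "To investigate interactions between diet groups and genotypes on bone mineral density (BMD) and hip fracture risk". Section 8.2 gives the method: "The adjusted model will also be further stratified by specific single-nucleotide polymorphisms (SNPs) of genes", the genes being PPARγ and "VDR, MTHFR, CYP24A1, CYP27B1, and IGF-1", and the stated purpose is "to explore potential gene-diet interactions". No SNP is named, and the number per gene is not given.

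The first paragraph of 8.2 describes how effect modifiers in general are handled. The model is stratified, and the authors "will add these covariates to adjusted models as interaction terms with diet group independently", with a likelihood ratio test of each. The end of 8.4 sets one threshold for the whole plan: "Two-sided p values < 0.05 will be considered statistically significant". No adjustment for multiple testing appears anywhere in the SAP.

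On ancestry, 8.1.3 says "Potential confounders are age at recruitment, sex, region, ethnicity, socio-economic status or education" and further items, with the final set to be informed by a DAG. Section 11.1.1 takes ethnicity from the touchscreen questionnaire: "We will regroup participants into the following ethnicity categories: White, Mixed race, Asian, Black, Other, and Unknown". The SAP mentions no genetic principal components, no restriction to one ancestry group and no product of ethnicity with diet group. Region is coded as three countries.

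**The concern.** Two separate features of the plan could each make a gene-diet interaction appear where there is none.

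The first is chance. Several candidate SNPs are examined against one uncorrected threshold, and because the SNPs are not listed, the number of looks is not fixed in advance.

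The second is population structure. Allele frequencies can differ by ancestry, and so can choice of diet. If the association of diet with fracture also differs by ancestry, carriers and non-carriers of an allele will show different diet hazard ratios simply because their ancestry mix differs. Adjusting for ethnicity as a main effect corrects the baseline hazard but does not remove this difference.

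At stake is how much weight a nominally significant gene-diet result can bear. The hazard ratios for diet group in the whole cohort do not depend on this analysis.

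**Working it through.** **The plan's own figure.** The SAP states no error rate or power for gene-diet interactions. Its only sample size figures are the minimum detectable hazard ratios for diet group in Section 6.0, Table 3. For vegetarians:

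- Events = 0.03 × 472,337 = 14,170.
- p = 8,685 / 472,337 = 0.0184; SD = √[p(1 − p)] = 0.134.
- HR = exp[(1.960 + 0.842) / (0.134 × √14,170)] = 1.19, as stated.

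(Table 3 prints an SD of 0.18 for this group; the hazard ratio follows from 0.134. That is a separate matter.)

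**Chance findings.** With m independent tests at 0.05 and no true interaction, the chance of at least one false positive is 1 − 0.95^m. The Bonferroni level is 0.05/m.

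| m | Basis | Chance of ≥ 1 false positive | Bonferroni level |
|---|---|---|---|
| 6 | six genes, one SNP each, one outcome | 26.5% | 0.0083 |
| 12 | as above with both outcomes, or two SNPs per gene with one outcome | 46.0% | 0.0042 |
| 18 | assumed three SNPs per gene, one outcome | 60.3% | 0.0028 |

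Only the first row rests on a count that 8.2 gives. The other rows depend on an unstated SNP count or on counting BMD as a second outcome. They also assume independence, whereas SNPs within a gene may be correlated, as may BMD and fracture, so they are upper-end values. Bonferroni brings the chance back to about 4.9% for 6 or 12 tests.

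**Ancestry.** Fitting the model separately by genotype, as 8.2 says, lets the ethnicity coefficient differ between genotypes. Within each genotype stratum, however, the diet hazard ratio is still an average over ancestries, weighted by the ancestry mix in that stratum. The missing element is a diet-by-ancestry term.

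The SAP gives no ancestry mix by diet group, no allele frequencies and no ancestry-specific diet effect, so the following is illustration on assumed inputs only. Compare the event-weighted mean diet HR in carriers with that in non-carriers, with no true gene-diet effect:

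- *Strong case.* 30% of vegetarians of a second ancestry; diet HR 1.4 in the first ancestry and 1.0 in the second; 20% and 70% carriers; equal baseline hazard. Carriers: (0.14 × 1.4 + 0.21 × 1.0) / 0.35 = 1.16. Non-carriers: (0.56 × 1.4 + 0.09 × 1.0) / 0.65 = 1.345. Ratio 0.86.
- *Mild case.* 10% of a second ancestry; HR 1.3 and 1.0; 30% and 60% carriers; baseline hazard in the second ancestry half that in the first. Carriers: (0.27 × 1.3 + 0.03 × 1.0) / 0.30 = 1.27. Non-carriers: (0.63 × 1.3 + 0.02 × 1.0) / 0.65 = 1.291. Ratio 0.98.
- *Same diet HR in both ancestries.* Ratio 1; this mechanism vanishes.

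To set this against precision: 3% of 8,685 vegetarians is about 260 fractures, and 3% of 247,571 regular meat-eaters is about 7,427. With a carrier share q, the standard error of the log ratio is √{[1/260 + 1/7,427] / [q(1 − q)]}, or 0.14 at q = 0.3 and 0.13 at q = 0.5 (assumed shares). Against that, a spurious ratio of 0.98 leaves the rejection rate of a single test at about 5%; 0.86 raises it to about 20%.

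**The case against.** The strongest reply is that the SNP sentence in 8.2 names no test. It says the model will be stratified, for exploration. A reader might infer that the SAP prescribes a SNP-by-SNP test at 0.05; it does not say so in those words. That reading comes from joining the opening paragraph of 8.2 to the threshold in 8.4. It is the natural reading, since an objective about interaction needs some rule for judging one, but it remains an inference. If no test is intended, the objective has no decision rule, which also needs settling.

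Second, the multiplicity concern is softened by the plan itself. The genes are six candidates chosen for plausibility, not a scan, and 8.4 commits to presenting every analysis and effect size. This stands in part: readers would see how many tests were made. It limits selective reporting but does not lower the error rate at 0.05. Whether exploratory tests in a cohort need formal correction is debated, which is a reason to ask for clear labelling as well.

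Third, the ancestry argument needs a diet effect that differs by ancestry, and nothing in the SAP shows one. Self-reported groups would also separate markedly different ancestries fairly well, and the adjustment set awaits the DAG. All of this is fair. It means the size is unknown and possibly small; it does not supply the missing diet-by-ancestry term.

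**Conclusion.** The point holds as a weakness in an exploratory secondary analysis. On the reading set out above, the chance of at least one false gene-diet interaction is about 26%, given one SNP per gene, one outcome, independent tests and no true interaction. It is higher with more SNPs or both outcomes, by an amount that depends on the unstated SNP count and on correlation. A reader might take 46% or 60% as the plan's error rate; the document does not fix the counts behind those figures.

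The ancestry part is qualitative. If the diet association differs by ancestry, a SNP-by-diet contrast can carry some of that difference, and the planned covariates do not prevent it. A reader might conclude that any reported gene-diet interaction would lack credibility. The document does not support that: the mechanism is conditional, its size cannot be derived from the SAP, the analysis is worded as exploratory, and all results are to be shown. The primary comparison of diet groups is untouched.

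**What to change.** Amend 8.2 as follows.

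1. List the SNPs in advance, with the genetic coding of each.
2. State one interaction likelihood ratio test per SNP and outcome, naming hip fracture and BMD explicitly.
3. Control the false discovery rate at 5% across those tests, or use Bonferroni (0.0083 for 6 tests, 0.0042 for 12), and label the results exploratory.
4. Fit the gene-diet models within the largest genetically inferred ancestry group, or add genetic principal components together with their products with diet group and with the SNP.

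This is a change of wording; genotype data are already in use, since 11.1.1 takes sex from genotyping. The costs are that some participants leave the genetic analysis if restriction is chosen, and that the per-SNP threshold is stricter. With the events in Section 6.0, the smallest detectable ratio of hazard ratios for vegetarians by a binary genotype, at 80% power and before any restriction, is exp[(z for α + 0.842) / √(14,170 × p(1 − p) × q(1 − q))], with p = 0.0184. For assumed carrier shares of 50% to 10%, it moves from about 1.42–1.79 at 0.05 to about 1.55–2.07 at 0.0083.
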